## 8.6 Steady-State Attainment

For Part 2 of the study, a repeated measures analysis of variance (RMA) will be carried out on ln-transformed pre-morning and evening dose (when applicable) concentrations (Days 2, 3, 5, 6, 8, 9, 11, 12, and 13) to determine attainment of steady state.

Repeated measures analysis of the last three pre-dose concentrations (Ln transformed) will be statistically analyzed using General Linear Model (PROC GLM) of SAS® version 9.4 software.

## 8.7 Pharmacodynamic Analyses

For Part 2 only, the WI-NRS measure will be used to determine the severity of itch experienced by subjects with hepatic impairment at screening. Subjects will complete the two WI-NRS forms (the “Nighttime Itch” and the “Daytime Itch”) at the same time during the screening visit and the average will be taken to determine the baseline severity.

For all Cohort 6 subjects, WI-NRS measure will also be performed on a daily basis from Day -1 to Day 16, twice a day, once within an hour of completing their morning and evening meals (if applicable). Subjects will fill in the “Nighttime Itch” form in the morning and the “Daytime Itch” form in the evening.

PD parameters will be summarized at each protocol scheduled time point, by actual treatment. Actual values and actual changes from baseline will be presented.

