Subjects:	
Up to a maximum of 94 adult male or female subjects, ≥ 18 and ≤ 80 years of age will be enrolled in the study. Subjects with normal hepatic function and hepatic impaired subjects may be non-smokers or light smokers (no more than 5 cigarettes/day).
 
Subjects who withdraw or are withdrawn from the study after dosing, for reasons other than safety and tolerability, may be replaced after consultation between the Investigator and Sponsor. The total number of subjects dosed (including potential replacement subjects) will remain within a maximum of 94 subjects for the whole study.
 
An effort will be made to carefully match the healthy subjects (Cohort 5, SAD) with the subjects with mild and moderate hepatic impairment (Cohorts 1 to 4) by age (± 10 years), BMI ($\pm 15\%$), and gender, to the extent possible. Matching strategy is to enroll control subjects with normal hepatic function who meet demographically matched mean criteria of the pooled subjects with mild and moderate hepatic impairment.
 
The study will enroll up to 8 subjects in Part 2 of the study (MAD) in each of the mild and moderate Child-Pugh categories (a total of up to 16 subjects). An effort will be made to enroll subjects who self-categorize as having some itch (Worst Itch Numerical Rating Scale [WI-NRS] mean score of ≥ 3 at screening). Worst itching intensity scores will be recorded twice daily as specified in the schedule of events. WI-NRS will be used to determine the severity of itch in the hepatic-impaired subjects.

Subject Distribution:	
Cohorts 1 to 4 (Part 1, SAD) will each include the following groups of hepatic-impaired subjects:

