	
and metabolite(s). The 90% confidence intervals (CIs) (Mild/Control, Moderate/Control, and Severe/Control) will be calculated for AUC_{0-t}, AUC_{0-inf}, and C_{max}. For these analytes, T_{max} will be analyzed non-parametrically with point estimates and 90% CIs for the median differences of T_{max} between groups (Mild-Control, Moderate-Control, and Severe-Control).
 
For Part 2 for each day (as appropriate), using GLM procedures in SAS, ANOVA will be performed on untransformed K_{el} and $T_{1/2\ el}$ and on ln-transformed AUC_{0-12}, AUC_{0-24}, AUC_{0-t}, AUC_{0-inf}, C_{max}, and C_{trough} at the alpha level of 0.05 for nalbuphine and metabolite(s).
 
For Part 2 of the study, a repeated measures analysis will be carried out on ln-transformed pre-morning and evening dose concentrations (when applicable) (on Days 2, 3, 5, 6, 8, 9, 11, 12, and 13) to determine attainment of steady state.
 
Within each group, dose proportionality will be assessed by a visual assessment of the individual and mean nalbuphine PK parameters. A power model analysis may also be performed to evaluate the doses-exposure, if warranted.
 
For the WI-NRS variables, post-dose scores will be assessed as an increment or decrement relative to the pre-dose baseline values. Each time point will be evaluated separately, relative to the baseline (pre-dose) value. Pair-wise comparisons among the groups will be made.
 
Review of interim safety analyses will be performed between cohorts or groups. Interim PK analyses may be performed between cohorts or groups if requested or warranted.
 
A complete description of the statistical analyses to be performed with the safety and tolerability data, as well as PK parameters will be presented in a Statistical Analysis Plan, which will be finalized prior to database lock.

--	---

3. List of Abbreviations

AE	Adverse event
ALT	Alanine aminotransferase
ANOVA	Analysis of variance
AST	Aspartate aminotransferase
AUC	Area under the curve
BMI	Body mass index
BUN	Blood urea nitrogen
CI	Confidence interval
CFR	Code of Federal Regulations
C _{max}	Maximum plasma concentration
C _{trough}	Last plasma concentration
COC	Combined oral contraceptives
CONMED	Concomitant medication
CP	Child-Pugh classification
CRF	Case Report Form
CV	Coefficient of variation
CYP	Cytochrome P450
DDI	Drug-drug interaction
DLT	Dose-limiting toxicity
ECG	Electrocardiogram
eGFR	Estimated glomerular filtration rate
FDA	Food and Drug Administration

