8.1 Sample Size

Up to a maximum of 94 adult male or female subjects, ≥ 18 and ≤ 80 years of age are planned to be dosed.

Subjects who withdraw or are withdrawn from the study after dosing, for reasons other than safety and tolerability, may be replaced after consultation between the Investigator and Sponsor. The total number of subjects dosed (including potential replacement subjects) will remain within a maximum of 94 subjects for the whole study (up to 78 subjects in the SAD and up to 16 subjects in the MAD).

The study will enroll up to 8 subjects in Part 2 of the study (MAD) with moderate Child-Pugh categories. An effort will be made to enroll subjects who self-categorize as having some itch (WI-NRS mean score of ≥ 3 at screening). Worst itching intensity scores will be recorded twice daily as specified in the schedule of events. WI-NRS will be used to determine the severity of itch in the hepatic subjects.

8.2 Inclusion Criteria for Subjects with Hepatic Impairment (Cohorts 1 to 4 and 6)

Subjects enrolled in this study will be members of the community at large. Subjects must meet all of the following criteria to be included in the study:

- 1) Male or female with stable hepatic impairment, non-smoker and/or light smoker (up to 5 cigarettes or equivalent/day), ≥ 18 and ≤ 80 years of age, with BMI ≥ 18.0 and ≤ 40 kg/m² and body weight ≥ 50.0 kg for males and ≥ 45.0 kg for females.
- 2) Physical signs consistent with a clinical diagnosis of liver cirrhosis (eg, liver firmness to palpation, splenic enlargement, spider angioma, palmar erythema, parotid hypertrophy, testicular atrophy, or gynecomastia) or prior liver biopsy showing hepatic cirrhosis or prior liver imaging (eg, computed tomography, ultrasound, magnetic resonance imaging) or laboratory tests consistent with hepatic cirrhosis.
- 3) Have mild (Child-Pugh class A, score of 5-6 points), moderate (Child-Pugh class B, score of 7-9 points), or severe (Child-Pugh class C, score of 10-15 points) hepatic impairment at screening.
- 4) The absence of clinically significant unstable cardiovascular, pulmonary, gastrointestinal, hematologic, neurological or psychiatric illness as determined by the Investigator.

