Also, for Part 2 of the study, a repeated measures analysis of variance (RMA) will be carried out on ln-transformed pre-morning and evening dose (when applicable) concentrations (Days 2, 3, 5, 6, 8, 9, 11, 12, and 13) to determine attainment of steady state.

Within each group, dose proportionality will be assessed by a visual assessment of the individual and mean nalbuphine PK parameters. A power model analysis may also be performed to evaluate the doses-exposure, if warranted.

In the event that hepatic impairment has a clinically relevant effect on nalbuphine and metabolite(s) PK, the relationship between measures of hepatic function and appropriate PK parameters (eg CL/F , AUC_{0-12} , AUC_{0-24} , AUC_{0-t} , AUC_{0-inf} , AUC_{0-t} , C_{trough} , and C_{max}) will be determined by a linear or non-linear regression.

Study results including the graphical description and the relationships between hepatic function and relevant PK parameters will be used to elaborate specific dosing recommendations if deemed clinically relevant.

For the WI-NRS variables, post-dose scores will be assessed as an increase or decrease relative to the pre-dose values. Each time point will be evaluated separately, relative to the baseline (pre-dose). Pair-wise comparisons among the group will be made if applicable.

Review of interim safety analyses will be performed between cohorts or groups. Interim PK analyses could be performed between cohorts or groups if requested or warranted.

A complete description of the statistical analyses to be performed with the safety and tolerability data, as well as PK parameters will be presented in the SAP, which will be finalized prior to database lock. Additional statistical analysis may be performed and will be described in the SAP.

13. Informed Consent

Potential subjects must provide written consent to participate after the nature, scope, and possible consequences of study have been explained in a form understandable to them.

An ICF that includes information about the study will be prepared and given to the subject. This document will contain all the elements required by the ICH E6 Guideline for GCP and any additional elements required by local regulations. The document must be in a language understandable to the subject and must specify who informed the potential subject. Where required by local law, the person who informs the potential subject must be a physician.

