#### **4. Changes from the Protocol**

No changes in planned analyses were done compared to the protocol.

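### SAP 8.7 reports WI-NRS change from baseline, but the only baseline it describes is a blended screening score, while the protocol sets a pre-dose reference

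*SAP*

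**What the plan says.** In SAP 8.7, Cohort 6 subjects complete the Nighttime and Daytime forms at the same screening visit, and "the average will be taken to determine the baseline severity". After that, "WI-NRS measure will also be performed on a daily basis from Day -1 to Day 16, twice a day", with the Nighttime form filled in each morning and the Daytime form each evening. The analysis statement is: "Actual values and actual changes from baseline will be presented". SAP 8.7 does not say which value is the baseline for those changes.

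The protocol states the reference for change separately. The synopsis says that "post-dose scores will be assessed as an increment or decrement relative to the pre-dose baseline values", and Protocol 12.3 says "Each time point will be evaluated separately, relative to the baseline (pre-dose". SAP section 4 states: "No changes in planned analyses were done compared to the protocol".

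The screening score also has a role in recruitment. Protocol 8.1 says "An effort will be made to enroll subjects who self-categorize as having some itch (WI-NRS mean score of ≥ 3 at screening". No WI-NRS threshold appears among the inclusion criteria in Protocol 8.2.

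**The concern.** A programmer working from SAP 8.7 alone finds one value called a baseline, the screening average, and could reasonably subtract it from every later score. For laboratory tests, vital signs and ECGs (SAP 7.3, 7.4 and 7.6) the SAP fixes baseline as the last result before drug. It gives no such rule for WI-NRS.

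Using the screening average would have three consequences:

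- **Mismatch.** A blend of night and day itch would be subtracted from separate night and day scores.
- **Age.** The screening window runs from Day -28 to Day -2, so the reference could be up to four weeks old.
- **Selection.** The score is the one used to favour itchier subjects, so on average it will tend to overstate their usual itch.

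Part 2 has no placebo or untreated group, so a fall produced by selection could not be told apart from a drug effect. The secondary objective on itch reduction rests on these data.

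**Working it through.** The documents give no planned effect, SD or power figure for WI-NRS, so there is nothing to reproduce. The two mechanisms can be sized with zero drug effect.

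**1. Night-day mismatch.** Let N and D be a subject's stable night and day scores. The screening baseline is (N + D)/2.

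- Night change: N - (N + D)/2 = (N - D)/2
- Day change: D - (N + D)/2 = -(N - D)/2

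If N - D = 2 (an assumed gap), the shifts are +1 and -1. They need no selection, and they cancel if the two forms are averaged over a day.

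**2. Regression to the mean.**

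*Input from the documents:* cut-off 3 on a 0-10 scale (Protocol 8.1 and Appendix 17.1).

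*Assumed, because the documents give none:* candidate mean 2 to 5, SD 2.0 to 2.5, test-retest correlation r of 0.5 to 0.9.

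If everyone enrolled scores 3 or more at screening:

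expected change = -(1 - r) x SD x phi(a) / (1 - Phi(a)), with a = (3 - mean)/SD.

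Example with mean 3, SD 2.5, r = 0.7: a = 0, phi(0)/(1 - Phi(0)) = 0.399/0.5 = 0.798, so the change is -0.3 x 2.5 x 0.798 = -0.60.

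Results for SD 2.5:

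| Mean | r = 0.5 | r = 0.7 | r = 0.9 |
|---|---|---|---|
| 2 | -1.34 | -0.80 | -0.27 |
| 3 | -1.00 | -0.60 | -0.20 |
| 4 | -0.70 | -0.42 | -0.14 |
| 5 | -0.46 | -0.28 | -0.09 |

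The smallest value on the grid is -0.06 (mean 5, SD 2.0, r = 0.9).

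This formula uses an unbounded normal distribution. With mean 2 and SD 2.5, about 21% of that distribution lies below 0, so a simulation on the bounded scale in half-point steps was also run (SD 2.5, means 2 to 4, r 0.5 to 0.9):

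- cut-off applied to every candidate: -0.13 to -1.18
- cut-off applied to a random half of candidates: -0.05 to -0.33
- cut-off not applied: about 0.00
- change taken from an independent Day -1 score: -0.01 to +0.01 in every scenario

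Across these scenarios the standard error of a mean change from screening is about 0.3 to 0.7 with 12 subjects and 0.25 to 0.6 with 16.

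**3. Which pre-dose scores exist.** WI-NRS is scheduled twice on Day -1, and confinement starts that morning. On Day 1, breakfast comes at least 2 hours after the dose (Protocol 9.7.1) and the morning form is tied to that meal (Protocol 9.9). The Day 1 Nighttime form is therefore normally completed after the first open-label dose, although its recall period ends at awakening (Appendix 17.1).

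**The case against.** The strongest reply is that the protocol already settles the matter. Protocol 9.9 contains the same screening-average sentence, and Protocol 12.3 separately sets a pre-dose reference for change. The average then reads as a descriptor of entry severity, and SAP section 4 carries the pre-dose rule forward. This is a fair reading, and it means that subtracting the screening average is not the settled plan. It does not close the gap. SAP 8.7 repeats the screening sentence and omits the pre-dose rule. Pre-dose alone does not separate screening from Day -1 either, since both precede dosing.

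Second, a score of 3 or more is a recruitment preference, not an eligibility rule, and every Cohort 6 subject is assessed whether itchy or not. That stands, and it is why the lower end of the selection bias is zero.

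Third, the stakes are limited. The study title calls the itch effect exploratory, SAP 8.7 is descriptive, and Part 2 may not be run. Actual values are shown at every scheduled time point, so Day -1 scores will be visible. One common baseline shifts every dose step equally, leaving within-subject differences between doses intact. All of this is right. Even so, the stated objective is a reduction in itch, and the summarised change from baseline is the figure most likely to be read as the answer.

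**Conclusion.** The point holds as an undefined and conflicting baseline. SAP 8.7 promises changes without naming the reference, and the only candidate it describes is a blended screening score tied to enrolment, against a pre-dose reference in the protocol.

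A reader might infer that the itch results will show improvement even if the drug does nothing. The documents do not support that. It would require the screening average to be the chosen reference and the enrolment preference to bind, and neither is established. Under those conditions the expected spurious fall is roughly 0.06 to 1.3 points with strict selection, smaller with partial selection, and nil if the preference does not bind. Much of that range is no larger than the sampling error of a cohort of up to 16. The figures rest on assumed mean, SD and correlation. The night-day shift depends only on the screening average being subtracted from each form and on night and day itch differing.

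**What to change.** Add to SAP 8.7, before database lock, a baseline rule by form:

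- **Night changes:** baseline is the Day -1 Nighttime form.
- **Day changes:** baseline is the Day -1 Daytime form.
- **Screening average:** used only to describe severity at entry.
- **Fallback:** if the Day -1 Nighttime form is missing, the Day 1 morning form may be used and flagged, because its recall is pre-dose but it is normally completed after dosing.

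The cost is a few sentences in the SAP, with no new data and no change to visits. The rule makes the comparisons like for like. It removes the selection artefact if errors in the Day -1 scores are independent of those at screening. Where screening falls only a day or two earlier, that may not fully hold and some artefact could remain. Placebo response and time trends are untouched, so the report should still say that Part 2 has no control group.

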## 8.8 Dose Proportionality

### 8.8.1 Part 1 (Single Ascending Dose)

For nalbuphine, PK parameters AUC0-t, AUC0-inf and Cmax dose normalized to 0.06 mg will be provided with descriptive statistics for each group. Mean AUC0-t, AUC0-inf and Cmax versus Dose will be presented graphically.

### 8.8.2 Part 2 (Multiple Ascending Dose)

For nalbuphine, PK parameters  $AUC_{0-t}$ ,  $C_{max}$ ,  $AUC_{0-12}$ ,  $AUC_{0-24}$ ,  $AUC_{0-inf}$ , and  $C_{trough}$  dose normalized to 0.06 mg will be provided with descriptive statistics for each group. Mean  $AUC_{0-t}$ ,  $C_{max}$ ,  $AUC_{0-12}$ ,  $AUC_{0-24}$ ,  $AUC_{0-inf}$ , and  $C_{trough}$  versus Dose will be presented graphically.

A power model analysis may also be performed to evaluate the doses-exposure, if warranted.

The power model will be used to investigate the dose proportionality using appropriate data from each Dose. For a PK parameter (P), the power model for a parallel design is

$$P = a \times Dose^b$$

where  $a$  is a multiplicative coefficient of the power model (it is related to the intercept when the model is ln-transformed) and  $b$  is the exponential coefficient of the power model (it corresponds to the slope when the model is ln-transformed). The 90% confidence intervals (CI) for  $b$  will be computed. The calculations will be performed on the ln-transformed scale using the Mixed procedure in SAS® for  $AUC_{0-t}$ ,  $C_{max}$ ,  $AUC_{0-12}$ ,  $AUC_{0-24}$ ,  $AUC_{0-inf}$ , and  $C_{trough}$ .

Dose proportionality will be evaluated prospectively according to the recommendations found in [Hummel et al. \(2009\)](#). For  $AUC_{0-t}$ ,  $C_{max}$ ,  $AUC_{0-12}$ ,  $AUC_{0-24}$ ,  $AUC_{0-inf}$ , and  $C_{trough}$  the 90% confidence intervals of  $b$  will be compared to the following exploratory bounds that depend on the dose range ratio ( $r$ =highest dose / lowest dose):

Lower bound =  $1 + \ln(0.5)/\ln(r)$  and

Upper bound =  $1 + \ln(2)/\ln(r)$ .

However, a more stringent criterion will be needed to conclude definitely at dose proportionality. Mean  $AUC_{0-t}$ ,  $C_{max}$ ,  $AUC_{0-12}$ ,  $AUC_{0-24}$ ,  $AUC_{0-inf}$ , and  $C_{trough}$  versus Dose will be presented graphically.

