5.2.1 Rationale for a Single- and Multiple-Escalating Dose Design

This study will include both a single-ascending-dose (SAD) portion and a multiple-ascending dose (MAD) portion. The PK, safety, and tolerability of single ascending doses (SAD) of NAL ER (4 dose levels) will be evaluated in subjects with mild and moderate hepatic impairment. Severe hepatic subjects will be evaluated at a single dose of 27 mg.

The purpose of the SAD will be to assess the safety and PK parameters of the given dose levels in hepatic impaired subjects relative to a selected healthy subject control population as part of the overall NAL ER development program. The SAD will also allow a better understanding of the safety, tolerability and expected steady state PK characteristics in mild and moderate hepatic impairment prior to undertaking safety and itch suppression efficacy studies in this patient population.

In the MAD portion of this study, PK assessment will be carried out at steady state at each respective dose level at steady state during the titration over 13 days up to the highest planned therapeutic dose of 162 mg. It is well documented, in clinical practice and the opiate literature, that gradually increasing the dose of drug with a structured titration can reduce the frequency and severity of the expected AEs associated with initiation of therapy. The NAL ER clinical program utilizes this type of structured titration strategy, starting with once per day dosing at the 27 mg dose of NAL ER, and increasing the dose in a stepwise manner over the next 13 days to the target investigational dose of 162 mg twice daily. Pharmacokinetic steady state is reached after 2 to 3 days of 162 mg twice daily.

Once the Part 1 SAD portion of the study is completed, if in the judgement of the Safety Committee the PK data demonstrates dose linearity across the dose range in both the mild and moderate hepatic impairment subjects (Group 1 and Group 2 subjects), such that PK modeling can be predictive of steady state dosing levels, a decision may be made to end the study without conducting Part 2 of the study.

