Based on the overall safety and tolerability observed in the subjects with mild and moderate impairment, at the completion of all doses tested, it will be determined by the Safety Committee whether or not it is safe to proceed with dosing for the first 2 subjects with severe Impairment. After review of the safety and tolerability for the first 2 severe subjects dosed at 27 mg, it will be determined whether or not to complete that dose level for the remaining severe subjects.

At the completion of all subjects dosed in the cohort, there will be an evaluation of safety and tolerability to determine whether to proceed to the next dose level for this group.

The Safety Committee will be composed of at least the Investigators and one medically qualified Sponsor representative. Some adjustments to the currently outlined doses and/or dosing regimen may be implemented by the Safety Committee, but the dose to be administered in a given dose cohort will not exceed the one currently outlined in the protocol.

Drug administration in Part 2 of the study (MAD) may be initiated following satisfactory review of the safety and tolerability data from Groups 1 and 2 (mild and moderate impairment) from Part 1 of the study (SAD) by the Safety Committee. Depending on safety and tolerability as well as on available PK data, the dose escalation scheme may be modified such that intermediate dose levels are administered. The dosage regimen (once daily versus twice daily) will be confirmed following review of PK data from Part 1 of the study (SAD).

If in the judgement of the Safety Committee the Part 1 PK data demonstrates dose linearity across the dose range in both the mild and moderate hepatic impairment subjects (Group 1 and Group 2 subjects), such that PK modeling can be predictive of steady state dosing levels, a decision may be made to end the study without conducting Part 2 of the study

In Part 2 of the study (MAD), subjects will receive a single 27 mg dose in the morning of Day 1. Starting on Day 2, doses will be subsequently escalated for each subject to twice daily, 12 hours apart, 27 mg, 54 mg, 108 mg, and 162 mg over 13 days. On the last treatment day, (Day 13), subjects will receive a single 162 mg dose in the morning. Subjects will remain at each dose level for 2-3 days (minimum 5 consecutive doses) with dose escalation predicated on tolerability of the prior dose (See Section [9.14.4](#) for dose escalation stopping rules).

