9.7 Study Restrictions

9.7.1 Food and Fluids

In Part 1 of the study (SAD), no food will be allowed from at least 8 hours before NAL ER dosing until at least 2 hours after. A standardized breakfast will be served at least 2 hours after NAL ER dosing. A lunch, supper, and a light snack will be served at appropriate times thereafter. Except for water given with NAL ER, no fluids will be allowed from 1 hour before dosing until 1 hour post-NAL ER dose.

In Part 2 of the study (MAD), on Days 1 and 13, no food will be allowed from at least 8 hours before dosing until at least 2 hours after dosing. A standardized breakfast will be served at least 2 hours after NAL ER dosing. For other dosing days, no food will be allowed from at least 2 hours before each dosing until at least 2 hours after dosing. Except for water given with IP, no fluids will be allowed from 1 hour before each dosing until 1 hour post-dose. Water will be provided *ad libitum* at all other times.

In addition, subjects will be required to abstain from:

- Food containing poppy seeds within 24 hours prior to admission and for the duration of the study;
- Food or beverages containing xanthine derivatives or xanthine-related compounds (coffee, black/green tea, chocolate) or energy drinks from 48 hours prior to first dosing until study exit;
- Natural health products (including herbal remedies, homeopathic and traditional medicines, probiotics, food supplements such as vitamins, minerals, amino acids, essential fatty acids, and protein supplements used in sport) from 7 days pre-first dose until study exit unless such products are deemed medically necessary for standard of care by hepatic impaired subjects;
- Food or beverages containing grapefruit, Seville orange, starfruit, pomegranate, pineapple, or pomelo from 14 days prior to first dosing until study exit.

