On Days 4, 7 and 10 a total of 9 blood samples will be drawn for quantification of nalbuphine and its metabolites in plasma from each subject for PK analyses as follows:

- At Day 4, 7 and 10 – pre-morning dose and at 1.50, 3.00, 4.00, 5.00, 6.00, 7.00, 9.00, and 12.0 hours post-dose (prior to the evening dose administration).

On Day 13 a total of 12 blood samples will be drawn for quantification of nalbuphine and its metabolites in plasma from each subject for PK analyses as follows:

- At Day 13 – pre- dose and at 1.50, 3.00, 5.00, 7.00, 9.00, 12.0, 24.0, 36.0, 48.0, 72.0 and 96.0 hours post- last dose.

Trough blood samples will be collected on Days 2, 3, 5, 6, 8, 9, 11, 12, and 13 prior to the morning and evening (if applicable) dose administrations.

Plasma concentrations on Day 1 from nalbuphine and its metabolites will be used to calculate the following parameters by standard non-compartmental methods:

- AUC0-12: Area under the concentration-time curve from time zero to 12 hours.
- AUC0-24: Area under the concentration-time curve from time zero to 24 hours.
- Cmax: Maximum observed concentration.
- Tmax: Time of observed Cmax.

Plasma concentrations on Days 4, 7 and 10 from nalbuphine and its metabolites will be used to calculate the following parameters by standard non-compartmental methods:

- AUC0-12: Area under the concentration-time curve from time zero to 12 hours.
- Cmax: Maximum observed concentration.
- Tmax: Time of observed Cmax.

Plasma concentrations on Day 13 will be used to calculate the following parameters by standard non-compartmental methods:

- AUC0-12: Area under the concentration-time curve from time zero to 12 hours.
- AUC0-24: Area under the concentration-time curve from time zero to 24 hours.
- AUC0-t: Area under the concentration-time curve from time zero to the last measurable concentration.
- AUC0-inf: Area under the concentration-time curve from time zero to infinity, calculated as AUC0-t + Ct/Kel, where: Ct = the last measurable concentration.
- Cmax: Maximum observed concentration.
- Ctrough: Concentration at the end of one dosing interval (tau = 12 hours)

$T_{max}$ :	Time of observed $C_{max}$ .

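### As specified, the Part 2 power model cannot be fitted for three of its six parameters and confounds dose with accumulation for a fourth; the steady-state test omits the last two troughs at 27, 54 and 108 mg

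*SAP*

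**What the plan says.** **Power model.** SAP 8.8.2 says "A power model analysis may also be performed to evaluate the doses-exposure, if warranted". It introduces the equation with "For a PK parameter (P), the power model for a parallel design is", names the SAS Mixed procedure without giving a subject term, and lists AUC0-t, Cmax, AUC0-12, AUC0-24, AUC0-inf and Ctrough. The 90% CI of the exponent b is compared with bounds of 1 + ln(0.5)/ln(r) and 1 + ln(2)/ln(r), where r is the highest dose over the lowest. The SAP calls these bounds exploratory and says a definite conclusion needs a stricter criterion. Plots of all six means against dose are planned unconditionally.

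**Design.** Protocol 9.4 states that "doses will be subsequently escalated for each subject to twice daily, 12 hours apart", so each subject passes through 27, 54, 108 and 162 mg.

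**Derived parameters.** SAP 8.4.2 says "Plasma concentrations on Days 4, 7 and 10 from nalbuphine and its metabolites will be used to calculate the following parameters", and the list that follows holds only AUC0-12, Cmax and Tmax. Day 1 adds AUC0-24. AUC0-t, AUC0-inf and Ctrough appear for Day 13 only.

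**Steady state.** Protocol 5.2.1 says "PK assessment will be carried out at steady state at each respective dose level". SAP 8.6 analyses pre-dose "concentrations (Days 2, 3, 5, 6, 8, 9, 11, 12, and 13) to determine attainment of steady state", then adds "Repeated measures analysis of the last three pre-dose concentrations (Ln transformed) will be statistically analyzed using General Linear Model". It does not say whether the last three are taken per dose level or over the whole study.

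**The concern.** The power model's parameter list does not match the parameters that the SAP derives at each dose, and its design label does not match the titration. An analyst following SAP 8.8.2 literally would have nothing to fit for three parameters. For a fourth, the slope could suggest more than proportional exposure because of accumulation alone.

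The steady-state test is planned, not optional. It is the check on the protocol's premise that each dose level is profiled at steady state, yet its day list leaves out the profile days for three of the four doses. With the window undefined, the analyst would have to choose it after seeing the data. Part 2 informs the secondary objective of selecting doses and dosing frequency in hepatic impairment.

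**Working it through.** The documents give no numerical result for either analysis, so there is no figure to reproduce.

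**1. Parameters by dose (SAP 8.4.2 and Table 3-2)**

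| Parameter | Days derived | Morning doses (mg) | r | Bounds for b |
|---|---|---|---|---|
| AUC0-t, AUC0-inf, Ctrough | 13 | 162 | 1 | undefined, ln(1) = 0 |
| AUC0-24 | 1, 13 | 27 (first dose), 162 | 6 | 0.613 to 1.387 |
| AUC0-12, Cmax | 1, 4, 7, 10, 13 | 27, 27, 54, 108, 162 | 6 | 0.613 to 1.387 |

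Bounds at r = 162/27 = 6: 1 − ln(2)/ln(6) = 0.613 and 1 + ln(2)/ln(6) = 1.387, a margin of 0.387 on each side.

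**2. Confounding in AUC0-24.** Protocol Table 2 gives an accumulation ratio of 1.61, and 50.88/31.53 = 1.614 reproduces it. If exposure is exactly proportional to dose and Day 13 carries that accumulation while Day 1 does not, b rises by ln(1.61)/ln(6) = 0.27, about 69% of the margin. The same table shows the shift in healthy subjects:
- Day 1 to Day 13: ln(351.15/31.53)/ln(6) = 1.345
- Day 4 to Day 13: ln(351.15/50.88)/ln(6) = 1.078

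These are AUC0-12 values, because the documents give no accumulation ratio for AUC0-24. They show the direction and rough size only.

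**3. Cost of leaving out the subject.** Half-width of the 90% CI for b = t(0.95, df) × σ / √(n × Sxx), where Sxx = 1.866 is the sum of squares of ln(27, 54, 108, 162) about their mean. Assumed CVs are 45% between subjects (Table 2 AUCtau: 33.7% to 54.1% on twice-daily dosing) and 20% within subjects. The protocol calls the latter lower but gives no figure.
- Observations treated as independent: σ = √[ln(1 + 0.45²) + ln(1 + 0.20²)] = 0.473, df = 4n − 2. Half-width 0.21 at n = 8 and 0.24 at n = 6.
- With subject effects: σ = √ln(1 + 0.20²) = 0.198, df = 3n − 1. Half-width 0.09 at n = 8 and 0.10 at n = 6. A within-subject CV of 15% to 30% gives 0.07 to 0.15 over these sizes.

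Each of these half-widths is below 0.387.

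**4. Troughs by dose level.** Each level has six doses.

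| Dose | Last listed trough | Collected but not listed |
|---|---|---|
| 27 mg | Day 3 PM, after dose 4 | Day 4 pre-dose and 12 h, after doses 5 and 6 |
| 54 mg | Day 6 PM, after dose 4 | Day 7 pre-dose and 12 h, after doses 5 and 6 |
| 108 mg | Day 9 PM, after dose 4 | Day 10 pre-dose and 12 h, after doses 5 and 6 |
| 162 mg | Day 13 AM, after dose 5 | no pre-dose trough omitted |

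The listed days allow three readings of SAP 8.6:
- All listed days together: the test spans a six-fold dose range.
- The last three overall: Day 12 AM, Day 12 PM and Day 13 AM, all at 162 mg.
- The last three listed at each level: doses 2, 3 and 4 at 27, 54 and 108 mg.

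None uses the two troughs that bracket the profiled interval at the three lower doses.

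**5. How much this matters.** Approach to steady state from zero after n doses 12 h apart is 1 − 2^(−12n/t½):

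| t½ | 2 doses | 4 doses | 6 doses |
|---|---|---|---|
| 6.6 h (Protocol 5.1.1.2) | 92% | 99% | 100% |
| 9.6 h (Protocol 5.1.1.2) | 82% | 97% | 99% |
| 20 h (assumed) | 56% | 81% | 92% |

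Carry-over from the previous level brings the escalated doses closer to 100%. The missing evening dose on Day 1 slows the 27 mg level slightly.

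**The case against.** The strongest reply is that the SAP claims little. The power model is optional, uses whatever data are appropriate from each dose, and is judged against exploratory bounds. AUC0-12 and Cmax are derived at all four doses: Table 2 means in healthy subjects give b of 1.09 and 1.07. The Mixed procedure is named, so a subject term is unspecified but not excluded. Ctrough is the 12 h concentration in the SAP, and that sample is already drawn on Days 4, 7 and 10, so its gap lies in the derivation list and not in the data. Part 2 may not run at all. All of this stands and limits the severity. It does not supply AUC0-t or AUC0-inf at a second dose, separate dose from accumulation in AUC0-24, or define the trough window.

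A reader might infer several stronger claims that the documents do not support:
- **Neither analysis can support any conclusion.** Two of the six parameters can be modelled, and 162 mg can be tested because Day 13 is listed.
- **Steady state at the lower doses is never tested.** That follows only if the last three troughs are taken over the whole study. A per-level reading tests troughs after doses 2 to 4, and dose 4 reaches about 97% to 99% at the documented half-lives.
- **The parallel-design label invalidates the slope.** With complete data it widens the interval and does not bias b.
- **Proportional AUC0-24 would fall outside the bounds.** At an 8.6 h half-life the simulated slope is 1.27 to 1.43 as the assumed absorption half-life goes from 0 to 4 h, so it straddles 1.387. Larger slopes need half-lives of 12 h or more, which the documents do not give.
- **Fasting differences bias Cmax 1.5-fold.** On days other than 1 and 13, Protocol 9.7.1 says "For other dosing days, no food will be allowed from at least 2 hours before each dosing until at least 2 hours after dosing". The 1.5-fold figure is for a high-fat, high-calorie meal against fasting; no effect is given for a 2-hour fast.

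**Conclusion.** The point holds for specification, and should be corrected before database lock. It does not invalidate Part 2.

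- The power model cannot be fitted as specified for AUC0-t, AUC0-inf and Ctrough. This follows from the text alone.
- For AUC0-24, accumulation could take about 0.27 of the 0.387 margin. This borrows the healthy-subject AUC0-12 ratio; the value in hepatic impairment is unknown.
- Treating observations as independent makes the CI for b roughly 2.4 times wider under the assumed CVs, but leaves the exploratory criterion within reach.
- Every reading of SAP 8.6 that keeps to its listed days misses the last two troughs at 27, 54 and 108 mg. The loss is small at documented half-lives and larger if hepatic impairment prolongs the half-life, which the trial is meant to find out.

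**What to change.** **SAP 8.8.2.** Fit ln(P) = ln(a) + b ln(dose) by group, with a random subject intercept, to AUC0-12, Cmax and the 12 h concentration from Days 4, 7, 10 and 13 only. Remove the parallel-design label. Drop Day 1, AUC0-24, AUC0-t and AUC0-inf from the model and from the plots against dose.

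**SAP 8.4.2.** Derive Ctrough on Days 4, 7 and 10 from the 12 h samples already drawn. Reconcile its definition with Protocol 12.1, which uses the last observed concentration.

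**SAP 8.6.** Run the test separately at each dose level on that level's last three troughs, adding the Day 4, 7 and 10 pre-dose and 12 h samples. At the three lower doses these follow doses 4, 5 and 6. Report the slope over time with a 90% CI.

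**For the sponsor to reconcile, or to note as a limit on comparing Cmax across days.** Fasting differs between profile days: at least 8 hours on Days 1 and 13 and at least 2 hours on the others, although Protocol 9.10.7 requires an 8-hour fast for laboratory tests, which fall on Day 10. Day 13 also lacks the 4 h and 6 h samples taken on Days 4, 7 and 10. No fasting rule is proposed here.

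**Cost.** SAP wording and programming; no new samples.
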